13.5 Secondary and Exploratory Objectives, Endpoints, Analysis Plans

For the continuous secondary endpoints (serum AFP, IL-6, serum DCA, liver stiffness, FIB-4 score, and MELD score) and exploratory endpoints, we will consider D(T) and D(P) as well as percent change relative to baseline, namely, D(T)/B(T) and D(P)/B(P). Biomarker levels at baseline and 6 months, as well as changes from baseline to 6 months, will be summarized using descriptive statistics and graphical methods. ANCOVA models with post-treatment value as the outcome, and treatment group and baseline value as predictors will be used to examine treatment differences. In these models, the estimated coefficient for treatment is the difference between the mean change scores of each arm [116]. Model fit will be assessed using standard model diagnostics including residual plots, influence statistics, and model assumptions such as normality and equivariance, will be verified. Potential outliers will be identified and reasons for extreme values will be investigated. Biomarker values may be transformed, e.g. logarithmically, to satisfy the normality assumption. Interaction between treatment group and baseline will be tested. Additional models that further adjust for other baseline characteristics, including routine clinical tests that have been shown to be strongly predictive of HCC diagnosis in prospective cohorts of cirrhosis such as higher alkaline phosphatase [6], lower platelets [6, 71, 73, 117], lower albumin [73, 118], and lower prothrombin activity [119]. We will also consider clinical variables representing important HCC risk factors captured through the epidemiological questionnaire (Appendix F), including body mass index, current alcohol use, and current dietary fat, carbohydrate, fiber, coffee, and antioxidants [99-112]. The change in variable criterion will be used to identify confounders for our final models. Model selection will be performed using the purposeful model selection approach [120], resulting in a parsimonious model that includes adequate control for confounding. Adjusted treatment effects will be

reported.

Analyses will be performed with R statistical software. All analyses will be conducted on an intention to treat basis (all randomized participants will be included in the assigned group) and will begin with univariate cross-sectional statistics for profiling the study population and bivariate tabulations as a preliminary step to possible model building. We will not control for overall Type I error due to small number of observations and the preliminary nature of the study.

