Liver stiffness. Recent studies have pointed to the predictive power of liver stiffness for HCC in patients with chronic hepatitis and/or cirrhosis [70-76]. Myofibroblasts are a major source of the hepatic extracellular matrix constituting the fibrous scar. Experimental studies have shown that statins can attenuate fibrosis by inhibiting activation, proliferation, and cytokine and collagen production of hepatic myofibroblasts [77, 78]. Figure 2. Plasma bile acid levels differ between cirrhotics with and without HCC. Log-transformed bile acid levels (pMoles/gram) in cirrhotics without HCC (blue dots), cirrhotics with HCC (red dots). Mean levels indicated by the gray bars. DCA=deoxycholic acid; GCA=glycocholic acid; TCDCA= taurochenodeoxycholic acid; GCDCA= glycochenodeoxycholic acid.

Furthermore, epidemiological studies have reported significant associations between statin use and fibrosis regression in patients with advanced fibrosis [39, 79, 80]. Reducing or reversing fibrosis and cirrhosis may create a less favorable environment for tumor development. FibroScan[®] examination is a non-invasive measurement of liver fibrosis. The advantage of FibroScan over biopsy is that it provides a look at the state of the liver globally, as opposed to a biopsy where only a very small sample is measured. A test result of >20 kPa (kilopascal) is generally associated with an increased HCC risk [81]. Another non-invasive measure of liver fibrosis is the Fibrosis 4 index (FIB-4) [82]. The FIB-4 index is calculated as follows: FIB-4 = (Age × AST (U/L)) ÷ (PLT (10⁹/L) × (\sqrt{ALT} (U/L)). High values of FIB-4 are associated with increased risk of hepatocellular carcinoma [83, 84]. Although there is limited data regarding statin use and liver stiffness, data show that statin use is significantly associated with a reduced risk of fibrosis progression among patients with chronic HCV infection [79, 85]. Thus, we will explore the secondary hypothesis that a statin intervention reduces liver stiffness as measured by FibroScan and the FIB-4 Index.

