Medical history, medications, and laboratory test results review. Medical history, concomitant medications, and laboratory test results will be reviewed at Study Visits 1, 2, 3, and 4 by one of the study hepatologists or the clinical research staff.

Vital signs and symptom assessment. Participants will have a vital signs and symptom assessment at Screen 1 and Study Visits 1, 2, 3, and 4. Each assessment will include an interval symptom history; ECOG performance status; vital signs, including blood pressure, heart rate, and temperature; and measurement of weight. Height will be measured at Study Visit 1. A physical assessment, including assessment of liver disease sequelae (varices, ascites, and encephalopathy) will be done at Screen 1 and Study Visit 4.

Blood specimen. A blood specimen (approximately 15 mL) will be collected from patients at the Screen 1 eligibility visit for blood tests to confirm eligibility. If a patient's lab results are current (within the past 30 days) in the medical record and within eligibility range, their blood will not be drawn at the Screen 1 visit. Otherwise, the patient's blood will be drawn to confirm eligibility. A Complete Blood Count and Automated Differential (CBDF), a Comprehensive Metabolic Panel (CMPL), and Prothrombin Time (PT/INR) will be done to confirm that blood levels are within the eligibility requirements (acceptable organ function, $AST/ALT \leq 5x$ upper limits of normal, and MELD ≤ 20).

A blood specimen (approximately 10-15 mL) will be collected from each participant at Study Visits 1, 2, 3, and 4 for laboratory blood tests to monitor for potential adverse effects of the intervention. A Lipid Panel and hemoglobin A1C will be done at Study Visits 1, 3, and 4. A Complete Blood Count and Automated Differential (CBDF) and Comprehensive Metabolic Panel (CMPL) will be done at Study Visits 2, 3, and 4. Creatine Phosphokinase (CPK) will be measured at Study Visit 1. Prothrombin Time (PT/INR) will be done at Study Visit 4 to calculate the MELD score. Clinical lab results from Screen 1 and Study Visit 4 will be used to calculate the MELD and FIB-4 scores.

An additional blood specimen (20 mL) will be collected from each participant at Study Visits 1 and 4 for research purposes. Ten mL of blood will be drawn for measurement of protocol-specific biomarkers (AFP, AFP-L3%, IL-6, and bile acids) and 10 mL of blood will be drawn for DNA extraction and use in future studies.

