7.6 Methods for Clinical Procedures

Blood specimen. A blood specimen (approximately 15 mL) will be collected from each participant at the Screen 1 eligibility visit for blood tests to confirm eligibility. If a patient's lab results are current (within the past 30 days) in the medical record and within eligibility range, their blood will not be drawn at the Screen 1 visit. Otherwise, the patient's blood will be drawn to confirm eligibility. Clinical labs will be done for a Complete Blood Count and Automated Differential (CBDF), a Comprehensive Metabolic Panel (CMPL), and Prothrombin Time (PT/INR). The CBDF includes tests for leukocytes, neutrophils, platelets, and hemoglobin; test results will be used to establish acceptable organ function necessary for trial eligibility. The CMPL includes tests for liver enzymes (AST/ALT); and for total bilirubin, creatinine, and sodium for calculation of the MELD score. Prothrombin Time is required for calculation of MELD. The CMPL and PT/INR test results will be used to confirm that blood levels are within the eligibility requirements (acceptable organ function, AST/ALT \leq 5x upper limits of normal, and MELD \leq 20).

A blood specimen (approximately 10-15 mL) will be collected from each participant at Study Visits 1, 2, 3, and 4 for blood tests to monitor for potential adverse effects of the intervention. The date and time of the blood draw and the participant's last meal will be recorded. A Lipid Panel and hemoglobin A1C will be done at Study Visits 1, 3, and 4. A CBDF and CMPL will be done at Study Visits 2, 3, and 4. Creatine Phosphokinase (CPK) will be measured at Study Visit 1. Prothrombin Time (PT/INR) will be done at Study Visit 4 to calculate the MELD score. See Appendix E for Clinical Laboratory Minimum Test Requirements.

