13.3 Accrual and Feasibility

Sample size: Intervention = 80 (40 statin: 40 placebo) randomized sample; Analytic sample = 72 (36:36)

after 10% drop-out. The expected accrual rate is 6-7 participants per month across four study sites, and the planned recruitment duration is 12 months. We anticipate that all evaluable participants will have completed all study procedures within 24 months. Power and precision arguments are provided below.

Accrual was calculated based on the number of liver transplant candidates actively registered at CSMC, NWU, GU, and UPR at a given time in addition to the number of new candidates expected to be registered over a 12-month period. Cirrhotics who are eligible and not listed for transplant may also be recruited.

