13.6 Reporting and Exclusions

We are anticipating a small proportion (10%) of drop-outs due to health deterioration, transplantation, or death. We are proposing to exclude patients with high MELDs to reduce this possibility. The median time to transplantation from waitlist registration nationally is approximately 16 months, thus we feel that the risk of transplantation in the newly registered patient population with low MELDs is very low [113]. Among patients who are already on the waitlist, there is certainly a risk for drop-out due to transplantation over a 6-month period, but we do not anticipate that this will be greater than 10%. We also anticipate some contamination from the simvastatin intervention to placebo due to non-compliance and this will be monitored and managed through blood tests. We do not expect cross-over from the placebo to the intervention group as participants will be aware that they might be on statins already and would not want to jeopardize their safety and care. However, the 2013 ACC/AHA clinical guidelines for prescription of statins may also influence drop-outs among participants who wish to reduce the risk of cardiovascular disease, LDL cholesterol \geq 190 mg/dL, and persons 40-75 years with diabetes or a 10-year cardiovascular disease risk \geq 7.5%. Most of these people would not meet the eligibility criteria for study participation. The drop-out rate is expected to be 10% from baseline to 6 months follow-up.

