APPENDIX E

Clinical Laboratory Minimum Test Requirements

Clinical labs will be done at Screen 1 to confirm eligibility for the trial; and at Study Visits 1, 2, 3, and 4 to monitor for potential adverse effects of the intervention. Labs must include at least the following tests. It is acceptable to do additional tests if they are included in the blood panels at your institution.

Blood Hematology: Complete Blood Count and Differential	Blood Chemistry: Comprehensive Metabolic Panel	Lipid Panel *	Other Blood Tests
Hemoglobin Platelet count Leukocytes (White blood cell count, total) Neutrophil count, absolute	Alanine aminotransferase (ALT (SGPT)) Aspartate aminotransferase (AST (SGOT)) Alkaline phosphatase (ALP) Bilirubin, total Creatinine Sodium Glucose Potassium Total Protein	Total cholesterol High density lipoprotein (HDL) cholesterol Low density lipoprotein (LDL) cholesterol Triglycerides	Hemoglobin A1C (HbA1C) * Prothrombin Time (PT/INR) † Creatine phosphokinase (CPK) §

* Lipid panel and hemoglobin A1C will be done at Study Visits 1, 3, and 4.

[†] Prothrombin Time will be done at Screen 1 and Study Visit 4 to calculate the MELD score.

§ Creatine phosphokinase (CPK) will be measured at Study Visit 1 to establish a patient-specific reference for this indicator of muscle toxicity. If the patient reports unexplained muscle pain or weakness during the trial, CPK will be tested again to check for elevation.

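### FIB-4 can be computed at months 1 and 3 from blood already drawn, but the planned month-6 ANCOVA ignores those values, so participants without a month-6 result contribute nothing and drop-out can bias the comparison

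*Combined protocol and SAP*

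**What the plan says.** Section 13.5 sets one model for the continuous secondary endpoints: "ANCOVA models with post-treatment value as the outcome, and treatment group and baseline value as predictors will be used to examine treatment differences". It adds that analyses follow intention to treat and cover everyone randomised. It names no method for missing values.

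Section 3 fixes the time points for FIB-4: "Clinical lab results from Screen 1 and Study Visit 4 will be used to calculate the MELD and FIB-4 scores". Sections 7.2.2 and 7.4.1 agree.

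Section 7.6 has the panels drawn more often: "A CBDF and CMPL will be done at Study Visits 2, 3, and 4". The schedule in Section 7.1 shows the same. Appendix E puts AST and ALT in the minimum chemistry panel and platelets in the minimum blood count.

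Section 13.6 expects losses and gives reasons: "We are anticipating a small proportion (10%) of drop-outs due to health deterioration, transplantation, or death". Section 13.3 turns this into an analytic sample of 72 of 80. Section 8.3 says that participants who stop the study agent are still followed where possible, with chart laboratory results collected at the scheduled time points and a 6-month visit if feasible.

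**The concern.** An ANCOVA on one post-treatment value can use only those who have that value. Someone who dies, withdraws or has no month-6 laboratory results leaves the FIB-4 comparison, even if the month-1 and month-3 results are on file. That does not match the commitment to analyse everyone randomised.

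The plan's own reasons for drop-out concern liver health, and a month-3 fibrosis score could plausibly predict such losses. If it does, the completers are a selected group and the treatment difference among them can be off. A model that also uses the earlier values corrects for selection that those values explain. The results it needs are already collected for safety.

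**Working it through.** **1. Can FIB-4 be computed at months 1 and 3?** Section 2.3 defines FIB-4 = (age × AST) ÷ (platelets × √ALT). All three laboratory inputs are in the Appendix E minimum panels, and both panels are done at Visits 2, 3 and 4. So yes. MELD cannot be added in this way, because it needs INR, which is drawn only at Screen 1 and Visit 4. The research biomarkers and liver stiffness are measured only at Visits 1 and 4.

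**2. Are those values after the first dose?** Sections 7.3.1 and 7.3.2 let a chart result up to 30 days old replace the draw. Taking 1 month as 30 days and 3 months as 90:
- Visit 2 earliest: 30 - 14 = day 16; a chart result could date from 16 - 30 = day -14, before treatment.
- Visit 3 earliest: 90 - 14 = day 76; a chart result dates from 76 - 30 = day 46 at the earliest, always on study.

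Month 3 is therefore dependable. Month 1 needs a check of the draw date.

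**3. How many are affected?** The plan's figure reproduces: 80 × 0.10 = 8 lost, 80 - 8 = 72 analysed. Eight is a planning figure for drop-out. The number without a month-6 FIB-4 could be smaller if chart results fill some gaps.

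**4. How large could the bias be?** The documents give no effect size, standard deviation or correlation for FIB-4, so all of these are assumptions: log FIB-4 with SD 0.5; correlations baseline to month 3 of 0.8, baseline to month 6 of 0.75, and month 3 to month 6 of 0.8 or 0.9; 40 per arm; half the effect present at month 3; all drop-out after month 3. Informative drop-out has log-odds -3.4 + 2 × standardised month-3 change, about 10% in an untreated arm.

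Two estimators were compared:
- Completer ANCOVA: Y6 = a + b·arm + c·Y0; estimate b.
- Likelihood using month 3: fit Y3 = a3 + d·arm + e·Y0 in everyone and Y6 = a6 + f·arm + g·Y0 + h·Y3 in completers; estimate f + h·d.

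Results (month 3 to month 6 correlation 0.8 / 0.9):

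| Drop-out | Truth | Completer ANCOVA | Using month 3 |
|---|---|---|---|
| Same mechanism in both arms | -0.20 | -0.194 / -0.189 | -0.201 / -0.200 |
| Same mechanism in both arms | 0 | -0.001 / -0.002 | about 0 |
| Placebo informative, simvastatin 10% at random | -0.20 | -0.178 / -0.167 | -0.201 / -0.201 |
| Placebo informative, simvastatin 10% at random | 0 | +0.023 / +0.035 | 0.000 |

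Attenuation:
- Same mechanism: 0.006/0.20 = 3% and 0.011/0.20 = 5.5%.
- Differing mechanism: 0.022/0.20 = 11% and 0.033/0.20 = 16.5%.

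The standard error is about 0.077, so the largest bias is 0.035/0.077 = 0.45 standard errors. Root mean squared error is equal for the two estimators under the same mechanism (0.077 and 0.077; 0.076 and 0.076). Under the differing mechanism it is 0.082 against 0.079, and 0.084 against 0.076. When drop-out is unrelated to FIB-4 there is no bias, and month 3 lowers the standard error by 1-3%.

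**5. Other assumptions.** A second simulation used standardised values, a month-6 effect of -0.53 SD (2.8/5.3, borrowed from the primary endpoint), adjacent correlations of 0.6-0.8 and 10% drop-out. The estimate with complete data was -0.532.
- Driven by month 3 in both arms: ANCOVA -0.523 to -0.526 (1-2% attenuation); repeated measures -0.533 to -0.534.
- Driven by month 3 in placebo only: ANCOVA -0.497 to -0.504 (5-7%); repeated measures -0.533 to -0.534.
- Driven by the unseen month-6 value: ANCOVA -0.486 to -0.500 (6-9%); repeated measures -0.494 to -0.510 (4-7% remains).

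**The case against.** A baseline-adjusted ANCOVA at one time point is a standard choice, and this is one secondary endpoint in a Phase II trial that calls itself preliminary. Section 13.6 gives a single list of drop-out reasons for all participants. On that reading the mechanism is the same in both arms, the attenuation is small, there is no false harm and mean squared error does not improve. This stands, and it is why the larger figures are labelled a worst case.

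A reader might infer that informative drop-out does bias the FIB-4 result. The documents do not support that: nothing in them says that placebo patients leave because they worsen while simvastatin patients leave at random. Bias is a conditional risk.

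A reader might also infer that everyone who leaves after month 3 is lost. Section 8.3 keeps following those who stop the agent, and Section 7.4.1 accepts chart results from the 30 days before Visit 4. FIB-4 is thus comparatively easy to recover at month 6. The loss is confined to deaths, withdrawals and participants without month-6 laboratory results.

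Lastly, a repeated-measures model does not by itself settle death or transplantation, both named in Section 13.6. It estimates the FIB-4 that would have been seen had the patient remained alive with the native liver. If departure follows deterioration after the last recorded value, most of the bias remains. Both objections stand and shape the fix.

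**Conclusion.** The point holds, at modest size. FIB-4 is computable from data already collected at months 1 and 3. The planned analysis discards those values, and a participant without a month-6 value is left out despite the stated intention-to-treat basis.

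Under the first set of assumptions, with about 10% informative drop-out after month 3, the completer ANCOVA is attenuated by about 3-6% if the mechanism is shared between arms. It is attenuated by 11-17%, or shows 0.02 to 0.04 log units of false harm under the null, in the constructed case where it is not. The second set gives smaller figures for month-3-driven drop-out. In the first set the bias never reaches half a standard error.

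These sizes rest on assumed correlations, SD, effect and drop-out mechanism. What does not depend on them is that the better analysis uses existing data at almost no cost. The primary analysis is untouched.

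**What to change.** In Section 13.5, for FIB-4 only, make the main analysis a mixed model for repeated measures on log FIB-4. Include arm, visit (months 1, 3 and 6), arm-by-visit, baseline and baseline-by-visit, with unstructured covariance. Include all randomised participants with at least one value drawn after the first dose, check draw dates for Visit 2 in particular, and report the month-6 contrast.

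State how deaths and values after transplantation are handled in the analysis, for example by excluding post-transplant values and naming the resulting estimand. Keep the month-6 ANCOVA as a sensitivity analysis. Leave AFP-L3%, MELD and the other secondary endpoints as planned.

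The cost is a short paragraph in 13.5 and a few lines of R, with no new samples or visits. The drawbacks are reliance on missing at random, only partial correction when drop-out depends on unseen values, and a model for FIB-4 that differs from that for the other secondary endpoints. Anyone with no value after the first dose is still not included, so the text should say so.

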13.6 Reporting and Exclusions

We are anticipating a small proportion (10%) of drop-outs due to health deterioration, transplantation, or death. We are proposing to exclude patients with high MELDs to reduce this possibility. The median time to transplantation from waitlist registration nationally is approximately 16 months, thus we feel that the risk of transplantation in the newly registered patient population with low MELDs is very low [113]. Among patients who are already on the waitlist, there is certainly a risk for drop-out due to transplantation over a 6-month period, but we do not anticipate that this will be greater than 10%. We also anticipate some contamination from the simvastatin intervention to placebo due to non-compliance and this will be monitored and managed through blood tests. We do not expect cross-over from the placebo to the intervention group as participants will be aware that they might be on statins already and would not want to jeopardize their safety and care. However, the 2013 ACC/AHA clinical guidelines for prescription of statins may also influence drop-outs among participants who wish to reduce the risk of cardiovascular disease, LDL cholesterol \geq 190 mg/dL, and persons 40-75 years with diabetes or a 10-year cardiovascular disease risk \geq 7.5%. Most of these people would not meet the eligibility criteria for study participation. The drop-out rate is expected to be 10% from baseline to 6 months follow-up.

13.7 Evaluation of Toxicity

All participants will be evaluable for toxicity from the time of their first dose of simvastatin. Presence or absence of toxicity will be registered as a binary variable. Comparison of assumed underlying rates between groups will be performed using Fisher's exact test, and exact confidence intervals will follow the Clopper-Pearson method.

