3. SUMMARY OF STUDY PLAN

Design Overview. We will conduct a randomized double-blinded, placebo-controlled Phase II trial of statin to reduce disease progression in 80 patients with liver cirrhosis enrolled at four study sites: Cedars-Sinai Medical Center (CSMC), Northwestern University Feinberg School of Medicine (NWU), Georgetown University/MedStar Georgetown University Hospital (GU), and the University of Puerto Rico Comprehensive Cancer Center (UPR). We will focus on patients with a current Model for End-Stage Liver Disease (MELD) \leq 20 to increase the likelihood that they will be healthy and transplant-free for the duration of the 6-month intervention and follow-up. Cirrhotics, given their high risk of developing HCC, have the potential to derive the maximum benefit from an intervention that could delay the progression to HCC.

Eighty patients will be randomized to simvastatin or placebo (40 in the simvastatin arm, 40 in the placebo arm). Assuming that ~10% of the study participants drop-out, we expect to have data on a final sample of 72 men and women (36 simvastatin, 36 control) completing the 6-month follow-up visit (Study Visit 4). Clinical and research measurements will be taken at baseline (Study Visit 1), month 1 (Study Visit 2), month 3 (Study Visit 3), and month 6 (Study Visit 4). The 6-month intervention duration was chosen because it corresponds to 1) mandated interval for clinical follow-up for those who are on the transplant waitlist, and 2) widely recommended interval for HCC surveillance in high risk cirrhotic patients based on tumor doubling time [95, 96]. In addition, a prior study showed that 6 months of statin intervention led to a decrease in serum AFP, which was not the case after only 3 months on statin [56].

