5.7 Adherence/Compliance

Compliance will be measured by pill counts and patient diaries. For telehealth visits, we will ask participants to photograph unused pills for remote pill counts and patient pill diaries and compliance will be assessed remotely. Compliance is defined as 85% of the total dose over the entire study period. A participant diary will be used to monitor daily compliance (Appendix C). Participants will be instructed to record the time the study drug was taken each day in the diary, as well as any potential side effects. Diaries will be reviewed and compliance will be assessed at Study Visits 2-4.

Phone calls will be made to study participants every four weeks (\pm 7 days) to monitor compliance. Participants will be asked if they missed any doses of medication, and the dates of all missed doses will be recorded. The study agent diary will be reviewed with participants at every visit. Participants who report having taken < 85% of the study drug doses between phone calls, or whose pill count at a study visit reveals < 85% compliance, will be called every two weeks (\pm 3 days) to monitor compliance.

The participant will be asked at registration if they would like to receive reminder emails or text messages regarding the study medication. Messages will be sent daily for the first week; in following weeks, messaging will be targeted to participants having difficulty remembering their dose. In addition, phone calls will be made to all study participants during the week before their final visit (Visit 4) to remind them to take the study drug every day until the last study visit. Participants will also be reminded to bring any leftover study drugs and the study diary with them to each visit.

Capsule counts will be performed at Study Visits 2, 3, and 4 to assess compliance. If less than 85% of the dose has been consumed during the study period, the subject will be considered non-compliant. All participants that receive a study agent for any period of time will be evaluable for toxicity.

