10.4 Tissue Banking

Biologic specimens collected during the conduct of each clinical trial that are not used during the course of the study will be considered deliverables under the contract and thus the property of the NCI. At study completion, NCI reserves the option to either retain or relinquish ownership of the unused biologic specimens. If NCI retains ownership of specimens, the Contractor shall collect, verify, and transfer the requested biologic specimens from the site to a NCI-specified repository or laboratory at NCI's expense.

11. **REPORTING ADVERSE EVENTS**

DEFINITION: AE means any untoward medical occurrence associated with the use of a drug in humans, whether or not considered drug related. An AE can therefore be any unfavorable and unintended sign), symptom, or disease temporally associated with participation in a study, whether or not related to that participation. This includes all deaths that occur while a participant is on a study.

Please note that all abnormal clinical laboratory values that are determined to be of clinical significance based on a physician's assessment are to be reported as AEs. Those labs determined to be of no clinical significance or of unknown clinical significance (per the physician's assessment) should not be reported as AEs. Any lab value of unknown clinical significance should continue to be investigated/followed-up further for a final determination, if possible.

A list of AEs that have occurred or might occur can be found in §6.2 Reported Adverse Events and Potential Risks, as well as the Investigator Brochure or package insert.

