11.1 Adverse Events

11.1.1 Reportable AEs

All AEs that occur after the informed consent is signed and baseline assessments are completed (including run-in) must be recorded on the AE CRF (paper and/or electronic) whether or not related to study agent.

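### Section 13.7 compares safety between arms only through a binary, undefined toxicity variable, so a moderate between-arm shift in ALT, AST, bilirubin or HbA1c could go unseen

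*Combined protocol and SAP*

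**What the plan says.** Section 13.7 gives the whole safety analysis. "Presence or absence of toxicity will be registered as a binary variable", and then: "Comparison of assumed underlying rates between groups will be performed using Fisher's exact test", with Clopper-Pearson intervals. It names no grade, attribution, organ class, event type, significance level or sidedness. On who counts, it says: "All participants will be evaluable for toxicity from the time of their first dose of simvastatin". Section 5.7 puts this differently: "All participants that receive a study agent for any period of time will be evaluable for toxicity".

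What can reach that variable is set in section 11. AEs are recorded "whether or not related to study agent" (11.1.1), and term, organ class, grade and attribution are collected for each (11.1.2). For laboratory results the physician decides: "Those labs determined to be of no clinical significance or of unknown clinical significance" are not to be reported as AEs.

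The laboratory series are drawn for safety. Section 3 says: "A Complete Blood Count and Automated Differential (CBDF) and Comprehensive Metabolic Panel (CMPL) will be done at Study Visits 2, 3, and 4". HbA1c is drawn at Visits 1, 3 and 4, and section 7.6 gives incident diabetes as a reason. Section 13.5 lists the continuous endpoints compared by ANCOVA at 6 months. FIB-4 and MELD are among them; ALT, AST, bilirubin and HbA1c as such are not.

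**The concern.** The plan can lose a safety difference in two ways.

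- **Dilution.** If toxicity is one yes/no per participant, a specific hepatic event shares the variable with every other event that counts. Section 7.3.3 asks about headache, nausea, abdominal pain and similar symptoms at each four-weekly call, so unrelated background events may be frequent in both arms.
- **Exclusion.** An enzyme or HbA1c change that spreads across an arm but is not judged clinically significant in any one person never becomes an AE, so it never reaches 13.7.

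The protocol itself shows why this matters. Section 2.3 names liver enzyme elevation and diabetes as the historical reasons for reluctance to prescribe statins in liver disease, and section 6.2 notes HbA1c increases with this drug class. The data that bear on both are collected, but the plan does not compare them by arm.

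**Working it through.** **Plan's own figure.** Section 13.7 states no rate, power or precision, so there is nothing to reproduce.

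**1. Which values are compared by arm, and where**

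| Value | Drawn | Planned between-arm use |
|---|---|---|
| ALT, AST | Screen 1, Visits 2, 3, 4 | Inside FIB-4, baseline and month 6 only |
| Bilirubin | Screen 1, Visits 2, 3, 4 | Inside MELD, baseline and month 6 only |
| HbA1c | Visits 1, 3, 4 | None |
| Any Visit 2 or 3 value of these | | None |

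**2. Does FIB-4 stand in for ALT and AST?** By the section 2.3 formula, at fixed age and platelets, multiplying AST by *a* and ALT by *l* multiplies FIB-4 by *a*/√*l*.

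- ALT ×2, AST ×1.3: 1.3/√2 = 0.92, an apparent 8% improvement.
- ALT ×2 alone: 1/√2 = 0.71.
- Both ×2: 2/√2 = 1.41, a worsening.

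FIB-4 falls whenever *a* < √*l*. With ALT doubled, that means AST rising less than 1.41-fold.

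**3. Does MELD stand in for bilirubin?** Doubling from 1 mg/dL or above adds 3.78 × ln 2 = 2.6 points to the base score. A rise from 0.5 to 1.0 adds nothing, because values below 1 are set to 1.

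**4. Cost of merging events.** The inputs are 40 per arm (section 3), Fisher's test (13.7), and an assumed two-sided 5% level. The event rates are assumptions, since the documents give none for this population. With hepatic rate *h* and an independent background rate *b* of other toxicity, equal in both arms, the merged rate is 1 − (1 − *b*)(1 − *h*). Power is by full binomial enumeration. For *h* = 5% v 20%:

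| Background *b* | Merged rates | Difference | Power |
|---|---|---|---|
| Event analysed alone | 5% v 20% | 15 points | 0.41 |
| 20% | 24% v 36% | 12 points | 0.15 |
| 40% | 43% v 52% | 9 points | 0.09 |
| 60% | 62% v 68% | 6 points | 0.05 |
| 80% | 81% v 84% | 3 points | 0.04 |

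Sensitivity to the assumptions:

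- 5% v 25%: 0.646 alone; 0.253, 0.145, 0.076, 0.045 merged.
- 2% v 15%: 0.363 alone; 0.127, 0.077, 0.048, 0.035 merged.
- 5% v 20% at a two-sided 10% level: 0.54 alone; 0.24, 0.14, 0.10, 0.07 merged.

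**5. A shift that produces no AE.** This is a separate question and is not comparable with step 4. For a 25% mean rise in ALT analysed by ANCOVA on the log scale, with 36 per arm and 69 degrees of freedom, the standardized effect is ln(1.25)/SD. Power at two-sided 5% is 0.88, 0.76 and 0.55 at assumed residual log SDs of 0.30, 0.35 and 0.45.

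**6. Is every Visit 2 value post-dose?** Visit 2 falls at 1 month ± 14 days, so as early as about day 30 − 14 = 16. Section 7.3.1 lets a result from the previous 30 days replace the draw, which reaches back to day 16 − 30 = −14. A Visit 2 value can therefore predate the first dose and could even be the Screen 1 sample.

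**The case against.** - **A reader might infer that the liver tests are never compared between arms.** The documents do not support that for ALT, AST and bilirubin at month 6, which enter FIB-4 and MELD and are analysed by ANCOVA. It is true of HbA1c and of all Visit 2 and 3 values.
- **A reader might infer that a hepatic signal would be missed.** That is too strong. Section 5.6 discontinues the agent permanently for related ALT or AST above 5 times ULN. Section 7.6 has the metabolic panel screened for AE-related issues. Section 8.5 stops accrual if 30% or more come off agent for probably or definitely related SAEs, after at least 15 are registered. Section 12.4 provides committee review. These should catch large individual signals, but none is a comparison of laboratory values between arms.
- **A reader might infer that nearly every participant will score positive.** Section 13.7 does not equate toxicity with any AE. If it means agent-related events, the background rate may be low. The word rates could also allow a per-event analysis, although no events are named. One yes/no per participant is the natural reading, not a stated one, which is why step 4 shows a range of backgrounds.
- **Section 11 is not a blanket exclusion.** Results of unknown significance are to be followed to a final determination, and clinically significant glycaemic changes can become AEs. A shift that is unremarkable in each individual still stays out.
- **The evaluability wording might be read as dropping placebo participants.** Section 5.7 shows that this is a slip.
- **Safety is not a listed objective (1.1 to 1.3), and the separate monitoring plan on file is not in these documents.** Both points stand. They argue for descriptive reporting, not for leaving the values unreported.

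**Conclusion.** The concern holds in a limited form. The only planned safety comparison between arms is a binary variable whose content is undefined. HbA1c and all Visit 2 and 3 liver tests have no by-arm analysis. FIB-4 and MELD cover part of the month-6 gap, but as efficacy scores, and FIB-4 can move in the favourable direction when ALT rises out of proportion to AST. What could be missed is a moderate between-arm shift, not a large individual one.

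Under the assumed rates, merging cuts power for a hepatic event from 0.36–0.65 to about 0.25 at best and 0.04 at worst. This rests on the one-variable reading, an equal and independent background, and a 5% level that the plan does not state. Even analysed alone, the event has only modest power at 40 per arm, so the gain from separating events lies in visible estimates and intervals rather than in a decisive test. The change is worth making because it needs no new data.

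**What to change.** Amend section 13.7 as follows.

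(a) Tabulate AEs by arm by term and organ class, by grade (including grade 3 or higher) and by attribution, with Fisher tests and Clopper-Pearson intervals by event type.

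(b) Report baseline-adjusted by-arm estimates with intervals (ANCOVA, log scale for the liver tests) for ALT, AST and bilirubin at Visits 2 to 4 and for HbA1c at Visits 3 and 4. Use only samples dated after the first dose, because of the 30-day substitution allowed at Visit 2.

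(c) Give worst post-dose CTCAE grade and shift-from-baseline tables, taken from the laboratory values whether or not they were reported as AEs.

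(d) Show AST, ALT and platelets by arm beside FIB-4.

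(e) Start evaluability at the first dose of study agent, to agree with section 5.7.

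The cost is some additional programming. No visit, sample or participant is added. The downside is more safety comparisons, which should be labelled descriptive; section 13.5 already disclaims overall Type I error control.
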